22.5 N/A

### **23.0 Local Number of Subjects**

23.1 One hundred percent of the subjects will be recruited locally. As stated in the inclusion/exclusion criteria, participants will be included for post-testing only if they achieve  $\pm 10$ bpm of their predicted maximum heartrate on the Bruce protocol. Participants will be informed of the study, screened, and consented to participate at one time. During testing, participants will be gathered until adequate power is reached.

23.2 The physical therapy class the participants will be drawn from has 37 students total. All willing participants will be screened and consented for inclusion, and data will be gathered until adequate power is reached.

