## **9.0 Procedures Involved\***

- 9.1 This study will be a repeated-measures design, with all participants undergoing both pre- and post-fatigue FSD test assessments. Two orthopaedic specialist physical therapists will perform the FSD assessments. The investigators will review scoring guidelines per the Park article, and will practice scoring the test prior to data collection to ensure good interrater reliability. Scores on the FSD test from each assessor will be averaged after data collection and prior to data analysis, with each assessor blinded to the other’s score prior to averaging the scores. Participants will be healthy physical therapy students. Fatigue will be induced via the Bruce protocol used in assessment of maximum cardiovascular capacity. The treadmill used is an HP Cosmos Quasar (HP Cosmos, Germany). The heart rate monitors used are Polar monitors (Polar Electro Inc, Bethpage, NY)
- 9.2 The FSD test grades the participant on movement quality during a repeated step down from a 20 cm step. The weight bearing leg will be the dominant leg (the leg the participant would use to kick a ball) as used in the Park et al experiment. The FSD test consists of five repeated movements of the forward step down, with one score given for the whole set of five repetitions. For each set of five movements, the rater observes and produces

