## 11.0 Data Management\* and Confidentiality

11.1 Since this study involves multiple repeated-measures over time, dealing with an ordinal level dependent variable, a Friedman's ANOVA would typically be used for data analysis. However, at least one previous study has analyzed this measure via parametric statistics, so we could potentially also pursue a Repeated Measures ANOVA if our data meets all parametric assumptions. Since our alternate hypothesis is two-tailed, our p-value will be divided by two for accurate significance assessment

11.2 To the investigators' knowledge, there is no previous literature examining the effects of an activity/intervention on a within-subjects change in performance on the FSD test. As a result, no within-subjects effects sizes were available for an a priori power-analysis for required sample size. In previous work examining the inter-rater reliability of the FSD test, Park, et al. used an effect size of 1.26, based upon the work of Rabin and Kozol, in which they measured the amount of ankle dorsiflexion and compared groups scoring differently on the FSD test in this anthropometric measure. We therefore, used 0.5 as our effect size because the current study design differs from the Rabin and Kozol study design, and given their large effect size the investigators felt justified in setting a moderate effect size for the power analysis. The power analysis used an alpha of .05 and power of .80 for a two-tailed hypothesis via a repeated measures, within factors ANOVA analysis. This power analysis determined the need for nine participants. With 37 students in the class, we have more potential participants than needed to ensure the required power to observe a statistical result if it exists.

11.3 The Excel sheet will be kept in in a password protected file on password locked computers in the PI and co-investigator's offices. Consent forms will be secured in a locked file cabinet in the PI's office.

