## 20.0 Resources Available

20.1 Both investigators have completed orthopaedic residencies and hold current licenses to practice physical therapy in the state of Louisiana. The co-investigator is an Orthopaedic Clinical Specialist, and the PI has recently taken the Orthopaedic Clinical Specialist exam and is awaiting results. PT licensure includes indications and contraindications for maximal exercise testing and prescription for various healthy and unhealthy populations. In addition, the PI has experience working with exercise testing at the Pennington Biomedical Research Center in Baton Rouge, LA. The co-investigator is currently completing his PhD work in Physical Therapy.

20.2 Describe other resources available to conduct the research: For example, as appropriate:

- The class of 2020 that will be enrolled in Exercise Physiology has a total of 37 students. With nine participants needed per the power analysis, there should be no difficulty recruiting the necessary number of participants.
- Both investigators are instructors in the School of Allied Health Professions in the Department of Physical Therapy, and have 30% of their time set aside for research purposes. This time will include recruitment and consenting of participants, testing, data analysis, and writing results for publication.
- The Faculty Practice Clinic in the School of Allied Health Professions is a functioning outpatient physical and occupational therapy clinic. It includes treadmills for aerobic testing, and the appropriate equipment to perform the FSD test. It also includes the emergency equipment necessary to be a functional clinic within regulation.
- The School of Allied Health Professions is part of the larger Health Sciences Center campus. Emergency transportation is available to the hospital, which is adjacent to the Medical School portion of campus. In addition, students have mental health services available for free through the School should this be necessary if a participant has an adverse psychological event to the testing procedures.
- All participants will give voluntary informed consent, by which they will be educated on what tests they will be expected to perform. Both investigators will be able to consent participants into the study. Both investigators will review the protocol prior to the testing sessions, and will keep independent records of FSD test. Prior to each testing sessions, the investigators will clarify any questions regarding

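### Does gathering data until power is adequate (section 23) let the results decide the sample size?

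*Protocol*

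**What the plan says.** Protocol section 4.0 (study-wide number) is marked not applicable, so section 23.0 is where the number of subjects would be expected. Section 23.1 reads "During testing, participants will be gathered until adequate power is reached", and section 23.2 reads "All willing participants will be screened and consented for inclusion, and data will be gathered until adequate power is reached". The only figure in section 23 is the class size, 37.

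The target is given elsewhere. Section 11.2 reports an a priori calculation at alpha .05 and power .80 for a repeated-measures ANOVA: "This power analysis determined the need for nine participants". It adds that, with 37 students, "we have more potential participants than needed to ensure the required power to observe a statistical result if it exists". Section 20.2 repeats the figure: "With nine participants needed per the power analysis, there should be no difficulty recruiting the necessary number of participants".

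Three other provisions bear on the point:

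- **Order of work.** Section 9.1: "Scores on the FSD test from each assessor will be averaged after data collection and prior to data analysis". Until then neither rater knows what the other gave. Section 11.5 has the two investigators record independently during testing.
- **Who reaches post-testing.** Section 23.1: "participants will be included for post-testing only if they achieve" the heart-rate target. Section 3.2 withdraws those who miss it before any post-fatigue test.
- **Whose data are removed.** Sections 13.2 and 13.3 drop anyone who does not complete the final Forward-Step-Down (FSD) test.

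**The concern.** A stopping rule stated in terms of power, not a count, raises two worries.

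1. **Data-driven stopping.** If power were recalculated from the scores as they came in, collection would tend to stop when the observed effect happened to be large. A nominal 5% test would then reject too often. The two investigators also rate the tests, and one of them does the statistics, so they would have the means to do it.
2. **Which nine.** If nine meant nine starters, any withdrawal would leave fewer than nine in the analysis and power below the section 11.2 target. Section 23 does not say that the nine must have completed every FSD test, and section 11.2 makes no allowance for losses.

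At stake would be the validity of the significance test in the first case and its power in the second.

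**Working it through.** **Step 1. Reproduce nine.** Inputs from the protocol: four measurements (one before the Bruce test and three after, section 7.1), effect size 0.5, power .80, alpha .05 (section 11.2). Assumed, because not stated: 0.5 is Cohen's f, correlation ρ between repeated scores, sphericity. The formula is the noncentral F with

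λ = n·m·f²/(1−ρ), df₁ = m−1, df₂ = (n−1)(m−1).

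Section 11.1 says "our p-value will be divided by two for accurate significance assessment", so alpha .025 was tried as well.

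- ρ = .5, alpha .025, n = 9: λ = 9·4·0.25/0.5 = 18, df 3 and 24, power .860. With n = 8, λ = 16 and power is .795, so nine is the smallest n that reaches .80.
- ρ = .3, alpha .05, n = 9: λ = 9·4·0.25/0.7 = 12.86, power .800. Nine again.
- ρ = .5, alpha .05: seven would be enough (λ = 14, df 3 and 18, power .813).

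Nine is thus a number computed before the study that standard inputs can reproduce.

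**Step 2. Type I error by reading.** Null simulations of a repeated-measures ANOVA with four measurements and normal errors, nominal .05:

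| Reading of the rule | Type I error |
|---|---|
| Stop at a fixed nine | 4.9% and 5.1% (two separate runs) |
| Test all 37 | 5.1% |
| Stop once observed power is at least 80%, looks from 9 to 37 | 7.6% (5 looks) to 9.9% (29 looks) |

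The last row needs a first look, a number of looks and an observed-power criterion. None of these is in the protocol. At nominal .025 the same rule gives 3.7% to 4.9%, above .025 but still under 5%.

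**Step 3. Which row applies.** Sections 11.2 and 20.2 give one number obtained in advance. Section 11.2 speaks of the required power as something secured by having enough students, so adequate power is reached by counting. Section 9.1 has the analysis variable, the average of the two raters' scores, formed only after collection. No interim analysis appears anywhere. The first row applies.

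**Step 4. Size of the evaluability gap.** Participants who miss the heart-rate target never reach post-testing (sections 3.2 and 23.1). Anyone removed under 13.2 or 13.3 is not in the analysis and adds nothing to its power, so counting that person would not satisfy section 23 as written. What section 23 does not spell out is the participant who meets the target but does not finish the ten-minute test. Power if such losses were wrongly counted towards nine:

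| Analysed | ρ .3, alpha .05 | ρ .5, alpha .05 | ρ .5, alpha .025 |
|---|---|---|---|
| 9 | .800 | .922 | .860 |
| 8 | .736 | .877 | .795 |
| 7 | .657 | .813 | .707 |

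The protocol gives no expected rate for this loss. The final test follows the Bruce test by ten minutes, on the same day and with no return visit.

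**The case for a change.** The strongest case for a change is that section 23 is the number-of-subjects section and contains no target. No sentence makes nine the point at which testing ends, and 23.2 consents every willing student, so a reader could expect any count from nine to 37. No sentence forbids using scores to decide when to stop. If nine starters were counted and 90%, 80% or 70% proved evaluable, mean power would be 74%, 66% or 58%, although students are plentiful and a clearer rule would cost a sentence or two.

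Part of this stands. Section 23 neither repeats nine nor says that those counted must have completed the final FSD test, and a cross-reference to 11.2 would read better.

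The rest does not carry. The uncertainty between nine and 37 does no harm to the error rate so long as the count does not depend on scores: it is about 5% at either end. Faulting the protocol for not forbidding an interim look it never plans is asking for detail that a protocol may leave to the statistical analysis plan. The 58% to 74% figures use assumed rates for all losses, including the heart-rate failures that 3.2 and 23.1 already keep out of post-testing. They also assume that nine gives exactly 80% power, which is only one of the settings that lead to nine.

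**Conclusion.** No change to the plan is called for. Read with sections 9.1, 11.2 and 20.2, section 23 means testing until the pre-calculated nine have contributed usable data, and an analyst following the protocol would do that. On this reading the type I error is 4.9% to 5.1% against a nominal 5%, and the analysed number meets the section 11.2 target. The 7.6% to 9.9% error rates belong to a procedure that the protocol does not describe. The remaining gap is one of wording and concerns a rare kind of loss. One such loss wrongly counted would leave power between .736 and .877, and in one of the three settings two losses would still leave it above .80.

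This rests on reading 0.5 as Cohen's f, on ρ between .3 and .5, and on sphericity and normal errors in the calculations. It concerns only the rule for ending data collection. It does not judge whether 0.5 is a suitable effect size or whether the halving in section 11.1 is right.

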### **24.0 Provisions to Protect the Privacy Interests of Subjects**

24.1 Due to the nature of the Bruce Protocol testing for the Exercise Physiology class, students will be visible to their classmates during testing. However, participants will have the ability to request screens be placed around the area where the FSD test occurs to ensure privacy.

24.2 Participants will be educated on the nature of the tests that they will be performing, as well as the risks and benefits associated with research participation. They will be allowed three minutes of familiarization prior to the pre-testing portion of the FSD test.

24.3 The investigators will inquire about past medical history in order to ensure the participant meets the inclusion criteria. Access to medical records is not otherwise required.

PROTOCOL TITLE: The Effect of Cardiovascular Fatigue on Performance of the Forward-Step-Down Test

**25.0 Compensation for Research-Related Injury**

25.1 N/A

25.2 N/A

**26.0 Economic Burden to Subjects**

N/A

**27.0 Consent Process**

27.1 Indicate whether you will be obtaining consent, and if so describe:

- Consent will take place in the classroom with all students present. Those wanting to participate will be screened with the ACSM medical screen, and there will be time for questions regarding the testing both as a group during the information and consent session, and individually by appointment with the PI or co-investigator within the one week following the informational session.
- Participants will be informed that they have up to one week to consent for the study after the general information is given. They will be given the contact information for both investigators, and both investigators will be able to consent a participant in the study.
- Participants will be reminded that they are able to withdraw at any time.
- The study will be following “SOP: Informed Consent Process for Research (HRP-090).”

***Non-English Speaking Subjects***

- N/A

***Waiver or Alteration of Consent Process (consent will not be obtained, required information will not be disclosed, or the research involves deception)***

- N/A

**Subjects who are not yet adults (infants, children, teenagers)**

- N/A

**Cognitively Impaired Adults**

- N/A

**Adults Unable to Consent**

PROTOCOL TITLE: The Effect of Cardiovascular Fatigue on Performance of the Forward-Step-Down Test

- N/A

**Adults Unable to Consent**

- N/A

**28.0 Process to Document Consent in Writing**

28.1 The study will follow “SOP: Written Documentation of Consent (HRP-091).”

28.2 Given the special population of students in this study, the investigators decided to obtain written informed consent.

28.3 Consent Document attached with ACSM medical screening to be performed at the time of informed consent.

